7.1.6 Progression-Free Survival

Progression-free survival (PFS) is defined as the duration of time from start of treatment to time of progression or death, the event that occurs first.

7.2 Safety/Tolerability

Analyses will be performed for all patients having received at least one dose of study drug. The study will use the CTCAE version 4.03 for reporting of non-hematologic adverse events (https://www.eortc.be/services/doc/ctc/CTCAE_4.03_2010-06-14_QuickReference_5x7.pdf) and modified criteria for hematologic adverse events.

8.0 ADVERSE EVENTS

8.1 ESK981 (formally known as CEP-11981)

8.1.1 Contraindications

Because of the potential for drug-drug interaction, the concurrent use of all other drugs, over-the-counter medications, and alternative therapies must be documented in the patient's record.

8.1.2 Special Warnings and Precautions for Use

ESK981 is metabolized via CYP1A2, CYP2C8, and CYP3A4. Inhibitors of CYP1A2, CYP2C8, and CYP3A4 have the potential to increase plasma concentration of ESK981. Inducers of CYP1A2, CYP2C8, and CYP3A4 have the potential to decrease plasma concentrations of ESK981. Concomitant use of a medication known to be a potent inhibitor of CYP1A2, CYP2C8, or CYP3A4, or a potent inducer of CYP1A2, CYP2C8, or CYP3A4 should be avoided unless deemed to be medically necessary by the investigator. In addition, nonclinical studies have identified the potential for ESK981 to inhibit CYP3A4/5 (K_i 2.2 μ M). ESK981 has the potential to increase plasma concentration of concomitant medications that are CYP3A4/5 substrates. Caution should be used, or alternative treatments considered, if concomitant treatment with CYP3A4/5 substrates that have a narrow therapeutic range is needed (see Appendix 2).

Adverse Reactions

- **Side effects:** The most frequently reported AE of any grade was fatigue (51%). Other frequently reported AEs ($\geq 20\%$ of patients) were nausea (47%), diarrhea (33%), decreased appetite (33%), abdominal pain (30%), back pain (28%), vomiting (28%), constipation (28%), headache (28%), dizziness (28%), and dyspnea (23%). These AEs were reported at a similar frequency between dosage cohorts, and no relationship with dose was evident.
- **Treatment-Emergent Adverse Events of Grades 3, 4, and 5 Severity:** Grade 3 or Grade 4 AEs occurred in 37% of patients across dosing cohorts ([32.6%] Grade 3 and [4.7%] Grade 4). Treatment-related Grade 3 or Grade 4 AEs were most frequent in the 97.4 mg/m² cohort. Grade 3 or Grade 4 laboratory hematologic toxicities were reported in 18.6 % of patients across dosage cohorts. The most common Grade 3 or Grade 4 laboratory hematologic toxicity was lymphopenia, which occurred across dosage cohorts (5.9, 29.6, 55.0, 97.4, and 126.6 mg/m²). Grade 4 leukopenia occurred in a single patient in the 126.6 mg/m² cohort. Grade 3 or Grade 4 neutropenia also occurred in two patients in the 97.4 mg/m² cohort (Grade 3) and in one patient in the 126.6 mg/m² cohort (Grade 4). No Grade 5 AEs occurred.
- **Serious Adverse Events** Serious adverse events (SAEs) occurred were deemed unlikely or not related to ESK981. Three patients (1 patient in the 97.4 mg/m² cohort and two patients in the 126.6 mg/m² cohort) experienced SAEs that were categorized as possibly or definitely related to ESK981: pyrexia, hemolytic anemia, hyperbilirubinemia, dyspnea, neutropenia, ECG change, and chest discomfort. There were no deaths occurred during the study.
- **Procedure in case of Pregnancy** The effect of ESK981 in pregnant and lactating women is not known, and the exposure of a fetus or nursing infant is considered a potential risk. ESK981 can cause fetal harm when administered to a pregnant woman based on its mechanism of action. Subjects receiving ESK981 are advised to use two acceptable methods of birth control (one of which must include a condom as a barrier method of contraception) starting at the time of screening for an ESK981 study and continuing throughout the course of treatment and for at least six months after ESK981 is discontinued.

If during the conduct of the clinical trial, a male subject impregnates his partner, the subject should report the pregnancy to the investigator. The investigator should report the pregnancy to the Coordinating Center as an SAE within 24 hours of awareness of the event. The expected date of delivery or expected date of the end

of the pregnancy, last menstruation, estimated fertility date, pregnancy result and neonatal data etc., should be included in this information.

The investigator should report the outcome of the pregnancy (independent of outcome, e.g., full term delivery, pre-term delivery, spontaneous abortion, induced abortion, stillbirth, death of newborn, congenital anomaly [including anomaly in a miscarried fetus, etc.] in accordance with the same reporting procedure as for SAEs. The date of outcome of the pregnancy, gestational age, date of birth and neonatal data etc., should be included in this information.

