Objectives	
Primary Objectives
 
 • To determine the clinical efficacy of ESK981 in combination with nivolumab therapy in patients with metastatic renal cell carcinoma. 
Secondary Objectives
 
 • To assess the clinical efficacy of ESK981 monotherapy in patients with metastatic renal cell carcinoma. • To determine the safety and tolerability of ESK981 monotherapy and in combination with nivolumab in patients with metastatic renal cell carcinoma. 
Exploratory Objectives
 
 • To determine the quality of life of patients enrolled on the study as reflected in patient-reported outcomes.
Number of Subjects	47 objective response evaluable patients
Inclusion Criteria	
 • Histologic diagnosis of renal cell carcinoma (any histology except medullary carcinoma or collecting duct carcinoma is acceptable) with radiologic or histologic evidence of metastatic disease. • Prior treatment with up to one (and only one) anti-VEGF or VEGFR inhibitor (small molecule or antibody). • Must have measurable disease as per Response Evaluation Criteria in Solid Tumors, version 1.1 (RECIST 1.1) criteria. • Must be of age \geq 18 years at time of informed consent. • Ability to understand and the willingness to sign a written informed consent. • Karnofsky performance status \geq 60. • Most recent systemic therapy or most recent radiation therapy \geq 2 weeks of first study drug dose. • Recovery to baseline or \leq Grade 1 CTCAE v.4.03 from toxicities related to any prior treatments, unless AE(s) are clinically non-significant and/or stable on supportive therapy.

	
 • Women of childbearing potential must have a negative serum or urine pregnancy test within 28 days prior to registration. Women of non-childbearing potential are defined as those who have no uterus, ligation of the fallopian tubes, or permanent cessation of ovarian function due to ovarian failure or surgical removal of the ovaries. All others are considered women of child bearing potential. • Adequate organ and marrow function.

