3.1 Inclusion Criteria

3.1.1 Histologic diagnosis of renal cell carcinoma (any histology except medullary carcinoma or collecting duct carcinoma is acceptable) with radiologic or histologic evidence of metastatic disease.

3.1.2 Prior treatment with up to one (and only one) anti-VEGF or VEGFR inhibitor (small molecule or antibody).

3.1.3 Must have measurable disease as per Response Evaluation Criteria in Solid Tumors, version 1.1 (RECIST 1.1) criteria.

3.1.4 Must be of age \geq 18 years at time of informed consent.

3.1.5 Ability to understand and the willingness to sign a written informed consent.

3.1.6 Karnofsky performance status \geq 60.

3.1.7 Most recent systemic therapy or most recent radiation therapy \geq 2 weeks of first study drug dose.

3.1.8 Recovery to baseline or \leq Grade 1 CTCAE v.4.03 from toxicities related to any prior treatments, unless AE(s) are clinically non-significant and/or stable on supportive therapy.

3.1.9 Women of childbearing potential must have a negative serum or urine pregnancy test within 28 days prior to prior to registration. Women of non-childbearing potential are defined as those who have no uterus, ligation of the fallopian tubes, or permanent cessation of ovarian function due to ovarian failure or surgical removal of the ovaries. All others are considered women of child bearing potential.

3.1.10 Adequate organ and marrow function as defined below:

System	Laboratory Value
Hematological	
Absolute Neutrophil Count (ANC)	$\geq 1.5 \text{ K/mm}^3$
Hemoglobin (Hgb)	$\geq 9 \text{ g/dL}$
Platelets (Plt)	$\geq 100,000/\text{mm}^3$
Renal	
Calculated creatinine clearance	Serum creatinine \leq 1.5 times the upper limit of normal OR creatinine clearance $>30\text{mL/min}$ by Cockcroft-Gault formula
Hepatic	
Total Bilirubin	$\leq 1.5 \times$ upper limit of normal (ULN)
Aspartate aminotransferase (AST)	$\leq 2.5 \times$ ULN ($\leq 3 \times$ ULN with known hepatic metastases)
Alanine aminotransferase (ALT)	$\leq 2.5 \times$ ULN ($\leq 3 \times$ ULN with known hepatic metastases)
Prothrombin time (PT) and activated partial thromboplastin time (aPTT) levels	$\leq 1.5 \times$ ULN (If patient is receiving anticoagulation that is expected to alter these levels, should be in targeted therapeutic range for that agent)

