- 3.2.10 The patient has received any investigational drug within 28 days prior to registration or 5 half-lives of the investigational drug, whichever is shorter.
- 3.2.11 History of bleeding disorders (e.g. pulmonary hemorrhage, significant hemoptysis, menometrorrhagia not responding to hormonal treatment) ≤ 6 weeks before Cycle 1 Day 1.
- 3.2.12 The patient is on a chronic daily medication known to be a severe or moderate inhibitor or inducer by Micromedex of CYP1A2, CYP2C8, or CYP3A4 at registration.
- 3.2.13 Systemic corticosteroids greater than the equivalent of 10 mg of prednisone or equivalent alternative steroid (except physiologic dose for adrenal replacement therapy) or other immunosuppressive agents (such as cyclosporine or methotrexate) and any other medications that could potentially impact the efficacy or safety of the study as judged by the treating investigator are NOT permitted from time of registration to subjects completing protocol therapy unless clinically indicated to manage adverse events or life threatening or serious conditions as determined by the treating investigator.
- 3.2.14 Have any condition that, in the opinion of the investigator, would compromise the ability of the subject to meet or perform study requirements.

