8.2 Nivolumab

Refer to the current package insert for nivolumab contraindications and adverse reactions.

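### The protocol names nursing-infant exposure to ESK981 as a risk, but Section 8.1.2 gives no breastfeeding instruction and no eligibility criterion excludes a breastfeeding woman

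*Combined protocol and SAP*

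**What the plan says.** Section 8.1.2, under the item on pregnancy, states that the effect of ESK981 in pregnant and lactating women is unknown and that "the exposure of a fetus or nursing infant is considered a potential risk". Two parties are named as possibly at risk: the fetus and the nursing infant.

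The instructions that follow are these:

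- Subjects are advised to use two forms of contraception, one of them a condom, from screening and "continuing throughout the course of treatment and for at least six months after ESK981 is discontinued".
- A pregnancy in a male subject's partner is to be reported to the Coordinating Center within 24 hours.
- The outcome of the pregnancy is to be reported in the same way.

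Section 8.1.1, headed Contraindications, consists of one sentence on recording concurrent treatments; it begins "Because of the potential for drug-drug interaction, the concurrent use of all other drugs". Criterion 3.1.9, repeated in the synopsis, reads in part "Women of childbearing potential must have a negative serum or urine pregnancy test within 28 days". Criterion 3.2.14 excludes a condition that in the investigator's opinion "would compromise the ability of the subject to meet or perform study requirements". For the second drug, Section 8.2 says only "Refer to the current package insert for nivolumab contraindications and adverse reactions". Section 3.0 requires every listed criterion to be met and allows no waivers.

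**The concern.** The protocol identifies a hazard to two third parties and writes controls for only one. Contraception and pregnancy testing protect a possible fetus. Neither does anything for an infant already being breastfed.

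Women of childbearing potential aged 18 or over may enrol, and a woman who has recently given birth can have a negative pregnancy test. ESK981 is taken by mouth as an outpatient, five days in every seven, until progression or intolerable toxicity (Sections 5.1 and 9.1). If the drug passes into milk, the infant's exposure would be repeated, not isolated. The synopsis plans two sites. One could decline or counsel a breastfeeding patient and the other could enrol her without comment, and both would be following the protocol.

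What is at stake is the safety of an infant and consistent handling across sites. The trial's efficacy conclusions are not at stake.

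**Working it through.** The point concerns absent text, so the check is a reading of every place where a control could sit. There is no figure in the plan to reproduce.

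**Eligibility criteria.** There are 10 inclusion criteria (3.1.1 to 3.1.10) and 14 exclusion criteria (3.2.1 to 3.2.14): 10 + 14 = 24. The number that mention breastfeeding, nursing or lactation is 0. The synopsis criteria also contain no mention.

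**Nearest provisions, compared with what would be needed.**

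| Provision | What it covers | Does it control infant exposure? |
|---|---|---|
| 3.1.9 and synopsis | Negative pregnancy test | No; the test does not detect lactation |
| 3.2.14 | Subject's ability to meet study requirements | No; no study requirement bars breastfeeding |
| 8.1.1 | Recording concurrent drugs | No |
| 8.1.2 | Contraception, pregnancy reporting | No; it names the risk without an instruction |
| 8.2 | Package insert, nivolumab only | Insert not supplied; it would not cover ESK981, and Cohort A receives no nivolumab |
| 5.3 and 5.6 | Prohibited therapies, off-treatment reasons | No mention; the best-interest reason in 5.6 concerns the patient |
| 6.1 and 9.1 | Assessment schedule, ESK981 drug information | No mention |

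The sentence in 8.1.2 is the only place in the supplied text that refers to lactating women or nursing infants.

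**Can the documents set the length of a no-breastfeeding period?** Only loosely. Table 2 in Section 1.2.3 gives day-15 half-lives. Five half-lives at the overall mean are 5 × 9.9 h = 49.5 h, and 49.5 / 24 = 2.1 days. The mean pools all doses. At 55 mg/m² and above, the listed values run from 11.0 to 14.7 h, which gives 5 × 11.0 = 55 h (2.3 days) to 5 × 14.7 = 73.5 h (3.1 days). The longest individual value printed is 20.6 h: 5 × 20.6 = 103 h, or 4.3 days. Individual values are printed only for very small dose groups, so a longer one may exist. These are plasma figures, and the documents give no data on transfer into milk. They show that the existing six-month contraception period far exceeds plasma washout, but they do not establish a breastfeeding interval. The sponsor must set that.

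**The case against.** The strongest reply is that part of the evidence is out of view. Consent pages were removed before review, and the Eligibility Worksheet, Investigator's Brochure and nivolumab package insert were not supplied. Section 8.4.3 shows that safety information is also placed in the brochure and the consent document. Advice not to breastfeed may be in one of them. This stands as a limit: the finding is that the instruction is missing from 8.1.2 and the criteria, not that the trial as a whole lacks it. It does not remove the gap in Section 3, which is fully present and governs enrolment.

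Second, registration is central (Section 4.0). The Coordinating Center reviews the worksheet and source documents for each patient, so sites do not act entirely alone. That is a real common checkpoint, but the protocol gives it no breastfeeding criterion to apply.

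Third, silence should not be read as a decision to allow breastfeeding. The same item in 8.1.2 writes its pregnancy-reporting trigger only for a male subject's partner, which suggests incomplete drafting. That is fair, and the conclusion does not depend on the authors' intent.

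Fourth, the practical effect is minimal, and an investigator remains free to decline or counsel such a patient. Both are true. They bear on the priority of the point, not on whether it is correct.

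**Conclusion.** The concern holds. Section 8.1.2 names a nursing-infant risk, and neither that section nor any of the 24 numbered criteria contains a breastfeeding instruction or exclusion. As written, the criteria do not keep a breastfeeding woman out of open-ended ESK981 dosing.

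The number affected is probably 0 or 1 of the 47 planned patients. That is an assumption, because the documents give no basis for an estimate. Sample size, error rates, the futility rule, the dose-limiting toxicity rules and the analysis are unaffected. The conclusion rests on the protocol text alone and makes no claim about the consent form, worksheet, brochure or the nivolumab label. It is a worthwhile, low-priority correction.

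**What to change.** 1. In 8.1.2, next to the contraception advice, add an instruction not to breastfeed during treatment and for a defined period after the last ESK981 dose. The six months already used for contraception is a convenient choice; the sponsor should confirm or replace it.
2. In Section 3.2 and the synopsis, add an exclusion for women who are breastfeeding and will not stop before the first dose.
3. Check that the Eligibility Worksheet and consent form say the same.

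The cost is one sentence, one exclusion line in two places and a consistency check, all of which can go into the next routine amendment. The effect on accrual should be negligible.

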5.0 TREATMENT PLAN

5.1 Treatment Dosage and Administration

Protocol treatment must start within 14 business days of enrollment to the study.

There are 2 cohorts for accrual with Cohort A being accrued first. Cohort B will follow and will have 2 stages of accrual. Cohort A will accrue 11 patients to ESK981 monotherapy treatment. Then Cohort B (combination therapy) will begin accrual of 17 patients to the first stage and if the interim analysis permits, the second stage will accrue an additional 19 patients.

5.1.1 Therapy with ESK981 will include starting dose of 160 mg (4 capsules) PO daily for 5 consecutive days followed by a 2-day off drug in each week, repeated weekly in 28 day cycles. Patients will continue treatment until disease progression or intolerable toxicity.

REGIMENT DESCRIPTION					
Agent	Premedications; Precautions	Dose	Route	Schedule	Cycle Length
ESK981	n/a	160 mg	PO	Once daily for 5 consecutive days of every week (5 days on followed by 2 days off)	28 days
Nivolumab (solution for injection)	Per institutional guidelines, none mandated.	480 mg/dose	IV infusion over 30-60 minutes with a sterile, nonpyrogenic, low protein binding 0.2 to 1.2 micrometer in-line filter. Follow with saline flush.	Day 1	28 days

Dose Level	Dose of ESK981	Dose of Nivolumab
Level 0	160 mg	Fixed at 480 mg flat dose
Level -1	120 mg	Fixed at 480 mg flat dose
Level -2	80 mg	Fixed at 480 mg flat dose

Dose-Limiting Toxicity (DLT)

Dose limiting toxicity (DLT) will be defined as any Grade 3 or higher toxicity (as defined by CTCAE 4.03) that occurs during the DLT evaluation period (Cycle 1 i.e. 28 days) EXCEPT laboratory abnormalities that are not clinically relevant or significant.

Subjects will be given a pill diary and instructed to complete it every cycle. Doses missed by 6 or more hours or vomited will be skipped and not made up but will be recorded on the diary as missed or vomited. The subject will be advised not to take any additional doses, but to wait for the next scheduled dose.

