Second episode of grade 2 or 1 st episode of ≥ grade 3 toxicity	Hold until resolved to ≤ Grade 1, then reduce by 1 dose level if available or discontinue if not available	Discontinue treatment
Third episode of grade 2 or 2 nd episode of ≥ grade 3 toxicity	Discontinue treatment	

Note: The drug modifications for toxicity only apply to the drug the toxicity is attributed to (i.e. the offending drug), and the other drug could be continued without modification.

Note: Any drug holds for toxicity can continue for a maximum duration of 12 weeks. Beyond that, the offending drug shall be permanently discontinued. The other drug can be continued.

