5.5 Duration of Therapy

In the absence of treatment delays due to adverse events, treatment may continue until one of the criteria listed in Section 5.6 apply. Patients will be followed for up to 24 months after removal from treatment or until death, whichever occurs first. Patients removed from treatment for unacceptable adverse events will be followed by phone call or clinic visit until resolution or stabilization of the adverse events.

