5.6 Off Treatment Criteria

Patients can be taken off study treatment at any time at their own request with a withdrawal of informed consent, or they may be withdrawn at the discretion of the investigator for safety, behavioral or administrative reasons. The reason(s) for discontinuation from study treatment will be documented and may include:

- Disease progression as defined in Section 7.0 or evidence of clinical progression as determined by treating investigator;
- Subject has intolerable toxicity from study therapy despite supportive measures and maximum permitted dose modifications and holds per protocol;
- Patient withdraws informed consent (termination of treatment and follow-up for any reason);
- Loss of ability to freely provide informed consent through imprisonment or involuntary incarceration for treatment;
- Patient is unable to comply with protocol requirements;
- Treating physician determines continuation on the study would not be in the patient's best interest;
- Development of second malignancy (except for basal cell carcinoma or squamous cell carcinoma of the skin or Gleason ≤ 6 prostate cancer) that requires treatment, which would interfere with this study;
- Lost to Follow-up. If a research subject cannot be located to document survival after a period of 2 years, the subject may be considered "lost to follow-up." All attempts to contact the subject during the two years must be documented;
- Termination of the study by the University of Michigan;
- Patient completes protocol treatment and follow-up.

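### The 24-hour pregnancy-reporting rule in 8.1.2 covers only a male subject's partner, and the only scheduled pregnancy test is at screening, although women of childbearing potential are eligible for a drug said to cause fetal harm

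*Combined protocol and SAP*

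**What the plan says.** On risk, section 8.1.2 states: "ESK981 can cause fetal harm when administered to a pregnant woman based on its mechanism of action". Everyone taking ESK981 is advised to use two contraceptive methods: "starting at the time of screening for an ESK981 study and continuing throughout the course of treatment and for at least six months", the six months being counted from the end of ESK981 treatment.

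On reporting, the same section gives one trigger: "If during the conduct of the clinical trial, a male subject impregnates his partner, the subject should report the pregnancy to the investigator". The investigator then reports that pregnancy as an SAE within 24 hours and later reports its outcome under the same procedure.

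On eligibility and testing, 3.1.9 reads: "Women of childbearing potential must have a negative serum or urine pregnancy test within 28 days prior to prior to registration". The Time and Events Table in 6.1 marks the pregnancy test once, in the screening column, whose window runs from day −28 to day −1. Footnote 2 to that table says only that urine or serum may be used. On the start of treatment, 5.1 says: "Protocol treatment must start within 14 business days of enrollment to the study".

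**The concern.** The warning in 8.1.2 is about giving the drug to a pregnant woman, but the reporting rule below it is written for a man's partner. Followed literally, a site must report a partner's pregnancy within 24 hours, while no sentence tells it to report the pregnancy of a woman who is herself taking ESK981. That is the more direct exposure, and it is the one for which the sponsor and the drug supplier most need prompt notice and outcome data.

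Testing is a related, smaller matter. A woman who conceives after a negative screening test can take her first dose with no further test. Advised contraception and the history and examination at C1D1 lower that risk, but they do not confirm that she is not pregnant when treatment starts.

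**Working it through.** The reporting part is a reading of the text. The testing part needs one date calculation. The plan gives no figure of its own to reproduce.

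**1. Is there a reporting duty for a female participant's pregnancy?** The sections that could create one are:

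| Section | What it covers | Explicit duty for a female participant's pregnancy? |
|---|---|---|
| 8.1.2, trigger sentence | A male subject's partner | No |
| 8.1.2, 24-hour and outcome sentences | Not limited by sex, but they refer back to the pregnancy in the trigger sentence | No separate trigger |
| 8.4.2, SAE definition | Lists congenital anomaly and important medical event, among others; does not name pregnancy | No; may apply to a later anomaly or by judgment |
| 8.6 and 8.6.1 | SAEs; 8.6 also covers unanticipated problems | No |
| 8.8, unanticipated problems | Needs all three: unexpected, at least possibly related, and suggesting more risk than already known | No; the third may fail because fetal risk is already stated |
| 5.6, off-treatment reasons | Does not name pregnancy; the list is open | No; this governs stopping treatment, not reporting |

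Explicit rules found in the available text: one for a male subject's partner, none for a female participant.

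**2. How old can the negative test be at first dose?**

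- Inputs: the screening window of day −28 to day −1 (6.1), and the next column in the table, which is C1D1.
- Reading: day −1 is the day before C1D1, so day −28 is 28 days before C1D1.
- Result: the test is between 1 and 28 days old at first dose.
- The rule in 3.1.9 counts 28 days back from registration. One test can satisfy both rules, so they do not conflict. Where both apply, the stricter limit governs, which is 28 days before C1D1.

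**3. How many tests are scheduled?** One at screening. None at C1D1, in later cycles, at end of treatment or in follow-up.

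**The case against.** The strongest reply is that a sensible site would report a female participant's pregnancy anyway. The heading of the procedure, the contraception advice and the outcome paragraph are not limited by sex. The important-medical-event category in 8.4.2 and the unanticipated-problem route in 8.8 are available by judgment. A treating physician can also stop the drug under the 5.6 reason that begins "Treating physician determines continuation on the study". This stands as far as it goes: a reader should not infer that such a pregnancy would necessarily go unreported or that treatment would have to continue. But each route depends on interpretation, whereas the partner's pregnancy has a plain rule with a deadline. The consent pages were removed, and 8.2 defers to a nivolumab package insert that is not included, so the finding is limited to the text available.

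On testing, the reply is that a C1D1 test is a preference: the plan already has a negative test, contraception from screening, and a clinical visit on the day of first dose. That is fair. No section requires a first-dose test, and a site may test as late as day −1. The extra test is therefore offered as an improvement, not as the correction of an inconsistency.

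Two stronger readings should be resisted.

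- A reader might add the 14 business days in 5.1 to the 28 days in 3.1.9. Fourteen business days are 18 calendar days from a Monday and 20 from any other weekday, ignoring holidays and taking registration and enrollment as the same day. That gives 28 + 18 = 46 to 28 + 20 = 48 days. The result holds only if the table's window sets no limit from C1D1. The layout points the other way, and 7.1.3 likewise counts baseline tumor evaluations, a different assessment, back from the start of treatment, to a limit of 4 weeks.
- A reader might infer from footnote 12 and 8.6.1 that pregnancy reporting stops 60 days after the last dose unless the event is judged drug-related. But 8.1.2 sets no causality condition and applies throughout the conduct of the trial, so those places need no repair.

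**Conclusion.** The point holds in two parts of different weight. The reporting gap is a real omission: the trigger in 8.1.2 leaves out the female participant, and nothing else in the available text explicitly puts her back. The testing point is a recommendation: one scheduled test, none at or after first dose, and a negative result that may be up to 28 days old when dosing begins.

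The 28-day figure assumes that the screening window is counted from C1D1, which the table implies but does not state. The conclusion that no test is required at first dose does not depend on that assumption.

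The documents do not say how many of the 47 planned response-evaluable patients would be women of childbearing potential, so the number affected is unknown. Response rate, sample size, power and type I error are untouched. The case for acting is that the possible harm is serious and the change is small.

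**What to change.** 1. Reword the trigger in 8.1.2 so that it applies when a female subject becomes pregnant as well as when a male subject's partner does. Keep the 24-hour SAE report, the outcome report and the coverage throughout trial conduct exactly as they are. The cost is one sentence and possibly a few extra reports.

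2. Require a negative urine or serum pregnancy test before dosing at C1D1 for women of childbearing potential, and mark it in the Time and Events Table. The cost is one test per such woman at a visit that already takes place, with the result needed before the first dose. This closes the interval between screening and first dose; it does not add detection during later cycles.
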